Appendix 3 Management and Discontinuation Criteria for Abnormal Liver Function Tests

Management and Discontinuation Criteria for Abnormal Liver Function tests have been designed to ensure subject safety and evaluate liver event etiology (see Guidance for Industry Drug-Induced Liver Injury: Premarketing Clinical Evaluation, FDA: July 2009) [33].

1. Abnormal Liver Chemistry Criteria:

The investigator or subinvestigator must review study subject laboratories to identify if any levels meet the following criteria:

- a. AST or ALT $> 5 \times$ ULN (if baseline ALT is \leq ULN);
- b. AST or ALT $> 8 \times$ ULN;
- c. AST or ALT $> 3 \times$ ULN and total bilirubin (TBL) $> 2 \times$ ULN or PT-INR > 1.5 , if PT-INR measured*;
- d. AST or ALT $> 3 \times$ ULN (if baseline ALT is \leq ULN) with signs or symptoms compatible with hepatitis or hypersensitivity (eg, fatigue, nausea, vomiting, right upper quadrant pain or tenderness, jaundice, fever, rash or eosinophilia [$> 5\%$])

OR

- e. AST or ALT $> 3 \times$ increase from baseline ALT or AST with signs or symptoms compatible with hepatitis or hypersensitivity (eg, fatigue, nausea, vomiting, right upper quadrant pain or tenderness, jaundice, fever, rash or eosinophilia [$> 5\%$])

* Unless an alternative explanation for PT-INR > 1.5 , such as the concomitant use of warfarin, is present.

2. Action to Be Taken by Investigator:

If any abnormal liver chemistry criterion is met, the investigator or subinvestigator must do the following:

[figure not shown]
- This event must be reported to the sponsor as soon as possible but no later than 72 hours of learning after its occurrence on the Liver Event Form.
- For criteria c, the case must also be reported as an SAE, unless an alternate explanation exists.
- Following the initial observed elevation, every effort should be made to have the subject return to the clinic within 72 hours to repeat liver function chemistries and for further hepatic evaluation.
- Every effort should be made to have the subjects monitored 2 to 3 times per week until liver function chemistries (ALT, AST, ALP, TBL) resolve, stabilize or return to within the normal range or to baseline levels.
- Consultation with a specialist such as a hepatologist is considered.
- Liver imaging (ie, ultrasound, magnetic resonance imaging [MRI], CT scan) is considered.

3. Follow-up Examination:

If any of the abnormal liver chemistry criteria are met, the following assessments should be performed at the follow-up visit(s) and documented in the Liver Event Form:

- Clinical sign and symptoms course
- Alcohol use
- Risk factors for nonalcoholic steatohepatitis (NASH) such as diabetes, obesity and hypertriglyceridemia
- Autoimmune hepatitis/cholangitis
- Wilson's disease
- Laboratory assessments
 - Viral hepatitis serology
 - Hepatitis A immunoglobulin M (IgM) antibody
 - Hepatitis B surface antigen (HBsAg) and Hepatitis B core antibody (HBc antibody)
 - Hepatitis C RNA
 - Hepatitis E IgM antibody
 - Cytomegalovirus IgM antibody
 - Epstein-Barr viral capsid antigen IgM antibody
 - For subjects with TBL of > 1.5 ULN, conjugated bilirubin should be measured
 - CBC with differential to assess for eosinophilia

Management and Discontinuation Criteria for Abnormal Liver Function Tests: Algorithm

- Following the initial observed elevation, every effort should be made to have the subject return to the clinic within 72 hours to repeat liver function chemistries and for further hepatic evaluation.
 - Subjects must be monitored 2 to 3 times per week until liver function chemistries (ALT, AST, ALP, TBL) resolve, stabilize or return to within the normal range or to baseline levels.
 - Consultation with a specialist such as a hepatologist is considered.
 - Liver imaging (ie, ultrasound, magnetic resonance imaging, computerized tomography) is considered.
 - When restarting drug, refer to the document content.
- * Unless an alternative explanation for PT-INR > 1.5, such as the concomitant use of warfarin, is present.
AE = adverse event; ALP = alkaline phosphatase; ALT = alanine aminotransferase; AST = aspartate aminotransferase; PT-INR = prothrombin time-international normalized ratio; SAE = serious adverse event; TBL = total bilirubin; ULN = upper limit of normal

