6.2 Concomitant Therapy During the Study

Concomitant therapy is defined as any therapy administered after administration of the first dose of cefiderocol until the EOS visit.

Cefiderocol will be administered in combination with a SOC treatment regimen.

Concomitant therapy, including prescription or nonprescription medications and procedures, will be recorded in the source documents and the eCRF and include the following information:

- Name of medication or procedure
- Start date
- Stop date
- Route of administration
- Reason for use

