7.6.5.6 Adverse Event Assessment of Clinical Laboratory and Other Safety Parameters

For any abnormal laboratory test results (hematology, blood chemistry, or urinalysis) or other safety assessments (eg, physical examination, vital signs) that occur or worsen following exposure to the study drug from baseline, the investigator or subinvestigator will consider whether those results are clinically significant. Abnormal laboratory test results are defined as values outside the reference range. For test results that are abnormal at baseline and significantly worsen following the initiation of the study, the investigator or subinvestigator must also consider whether those results are clinically significant. Any test results that are considered to be clinically significant by the investigator or subinvestigator are to be recorded as AEs in the source documents and the eCRF. If abnormal laboratory finding is associated with disease or organ toxicity, the investigator should report only the disease or organ toxicity as an AE. These AEs should also be assessed as to whether or not they meet the definition of serious and should be reported accordingly.

The investigator or subinvestigator will consider test results to be clinically significant in the following circumstances (at their own discretion in the other circumstances):

- Clinical laboratory test results that lead to any of the outcomes included in the definition of an SAE (see [Section 7.6.5.7.1](#))
- Clinical laboratory test results that lead to a change in dosing of study drug or discontinuation from the study
- Clinical laboratory test results that lead to a concomitant medication treatment or other therapy
- Clinical laboratory test results that require additional diagnostic testing (except for a confirmatory test) or other medical intervention
- Clinical laboratory test results that meet the management and discontinuation criteria for abnormal liver function tests or transaminase elevations identified in [Appendix 3](#).

In addition, when any test result meets the management and discontinuation criteria for abnormal liver function tests ([Appendix 3](#)), the results of further assessments and required follow-up should be recorded in the Liver Event Form.

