7.6.5.7 Serious Adverse Events

7.6.5.7.1 Definition

An SAE is defined by regulation as any AE occurring at any dose that results in any of the following outcomes:

- Death
- Life-threatening condition
- Hospitalization or prolongation of existing hospitalization for treatment

- Persistent or significant disability/incapacity
- Congenital anomaly/birth defect
- Other medically important condition

Important medical events that may not result in death, be life-threatening, or require hospitalization may be considered an SAE when, based upon appropriate medical judgment, they may jeopardize the subject and may require medical intervention to prevent 1 of the outcomes listed in this definition. Examples of such medical events include allergic bronchospasm requiring intensive treatment in an emergency room or at home, blood dyscrasias or convulsions that do not result in inpatient hospitalization, or the development of drug dependency or drug abuse. The investigator or subinvestigator will determine the seriousness of an AE. Clinical laboratory liver test results that meet the following criteria are considered to be an SAE (See [Appendix 3](#)):

Test result in which aspartate aminotransferase (AST) or alanine aminotransferase (ALT) > 3 x the upper limit of normal (ULN) and TBL > 2 x ULN.

Hospitalization for preplanned procedures or for an elective procedure not associated with a worsening of a known underlying medical condition is not considered an AE, and therefore will not be considered an SAE despite requiring hospitalization. However, complications of a procedure will be considered an AE and hospitalization or prolongation of a hospitalization for reasons other than an AE would not be considered an SAE.

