7.6.5.7.2 Reporting Serious Adverse Events

All SAEs must be reported to the CRO or sponsor in detail on the SAE Form or via electronic data capture (EDC) within 24 hours from the time point when the investigator first becomes aware of the SAE. If EDC becomes unavailable, all SAEs must be reported to the CRO or sponsor in detail utilizing the SAE form. All SAEs must be reported regardless of causal relationship to the study drug. A sample of the paper SAE Form and further instructions can be found in the Site Regulatory Binder. Follow-up information on the SAE may be requested by the sponsor.

When reporting SAEs, the investigator should record the diagnosis whenever possible. If no diagnosis is available at the time of reporting, individual signs and symptoms can be reported.

In the event of any SAE reported or observed during the study, whether or not attributable to the study drug, site personnel must report the SAE via the EDC or if the EDC is unavailable, prepare an SAE Form and fax or e-mail the completed form within 24 hours to:

OR

If the sponsor requires a follow-up assessment, the investigator should enter new information into the EDC or by using the SAE Form if the EDC is unavailable. Discharge summaries, consultant reports (from other departments or other hospitals), autopsy reports, or other relevant documents must be evaluated by the investigator and all relevant information must be reported. Copies of these reports may also be requested by the sponsor; however do not send hospital medical records to the sponsor unless specifically requested.

Appropriate remedial measures should be taken by the investigator using his/her best medical judgment to treat the SAE. These measures and the subject's response to these measures should be recorded in the source documents and the eCRF. Clinical, laboratory, and diagnostic measures should be employed by the investigator as needed to adequately determine the etiology of the event.

Any SAE occurring after AE assessment period specified in [Section 7.6.5.2](#) that is considered to be related to the study drug by the investigator, must be reported to the CRO or the sponsor.

The investigator will be responsible for reporting all SAEs to the IRB with the local regulatory requirement, as well as the sponsor. The sponsor will be responsible for reporting SAEs to the regulatory authorities as required by the applicable regulatory requirements.

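### Appendix 3 waives an SAE report that Section 7.6.5.7.1 requires, and its criterion a tests baseline ALT even for AST, so one type of sign-free AST rise meets no liver criterion

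*Protocol*

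**What the plan says.** **SAE rule.** Protocol Section 7.6.5.7.1 treats AST or "alanine aminotransferase (ALT) > 3 x the upper limit of normal (ULN) and TBL > 2 x ULN" as an SAE and points to Appendix 3. Section 7.6.5.7.2 requires every SAE to be reported "within 24 hours from the time point when the investigator first becomes aware of the SAE", whatever its causal relationship to study drug. Criterion c in Appendix 3 covers the same enzyme and bilirubin combination and adds a second arm, PT-INR above 1.5 if measured. Its action list then says: "For criteria c, the case must also be reported as an SAE, unless an alternate explanation exists". Any case meeting a liver criterion also goes to the sponsor as soon as possible and "no later than 72 hours of learning after its occurrence on the Liver Event Form".

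**Liver criteria.** In Appendix 3:
- a: AST or ALT above 5 × ULN
- b: AST or ALT above 8 × ULN at any baseline
- c: as above
- d: AST or ALT above 3 × ULN with compatible signs or symptoms
- e: a rise of more than 3 × from baseline with such signs or symptoms

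Criteria a and d apply to either enzyme, but their condition, "ULN (if baseline ALT is" no higher than ULN, names ALT alone.

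**Consequence of meeting a criterion.** Section 7.6.5.6 lists the results that must count as clinically significant, and so be recorded as AEs. Among them are "Clinical laboratory test results that meet the management and discontinuation criteria for abnormal liver function tests or transaminase elevations identified in" Appendix 3. Results outside the listed circumstances are judged by investigators "at their own discretion in the other circumstances".

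**The concern.** The first problem is that two parts of one protocol answer the same question differently. For raised transaminases with raised bilirubin and another plausible cause, a site following Section 7.6.5.7.1 files an SAE within 24 hours. A site following Appendix 3 need not file one. This also decides whether the case appears among the SAEs, which SAP Section 9.3.1 presents as listings without summary tables. The situation is plausible here: subjects are ventilated for pneumonia, and "Cefiderocol will be administered in combination with a SOC treatment regimen", so other causes of abnormal liver tests will often be candidates.

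The second problem is a trigger tied to the wrong enzyme. A raised baseline ALT is a reason to be cautious about a later ALT value. It is no reason to switch off the 5 × ULN trigger for AST when AST started normal. Section 4.3 sets no liver-enzyme limit, so subjects with a raised baseline ALT can enrol. A result that meets no criterion does not trigger the Liver Event Form, the follow-up work-up or automatic clinically significant status.

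**Working it through.** No sample size or power figure bears on this, so the check is a comparison of rules. Enzymes and TBL are in multiples of ULN.

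**1. SAE rule.** Section 7.6.5.7.1: SAE if (AST or ALT > 3) and TBL > 2. Appendix 3: SAE report if (AST or ALT > 3) and (TBL > 2 or PT-INR > 1.5), and no other explanation.

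| ALT | TBL | PT-INR | Other explanation | 7.6.5.7.1 | Appendix 3 |
|---|---|---|---|---|---|
| 4 | 2.5 | 1.0 | no | SAE | SAE report |
| 4 | 2.5 | 1.0 | yes | SAE | report waived |
| 4 | 1 | 1.8 | no | not listed | SAE report |
| 4 | 1 | 1.8 | yes | not listed | report waived |

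The second row is the contradiction. In the third row Appendix 3 adds a case that the definition does not mention. That extends the definition without contradicting it.

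Outer reporting limits: 72 − 24 = 48 hours. The Liver Event Form is due as soon as possible, so 48 hours is the most by which the limits differ.

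**2. Criterion a.** Take baseline AST 0.8 and baseline ALT 1.1 (ALT unchanged), then AST 7, no signs, normal TBL and PT-INR. The rise is 7 / 0.8 = 8.75-fold.
- a: 7 > 5, but baseline ALT 1.1 > 1, so not met
- b: 7 is not above 8, so not met
- c: TBL and PT-INR normal, so not met
- d and e: both need signs or symptoms, so not met

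With baseline ALT 1.0 instead, the same AST rise meets a. With signs, it meets e. At AST 8.1 it meets b, and with TBL 2.5 it meets c.

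On a grid (baseline AST 0.3 to 1.0; baseline ALT 1.1, 2 or 4; AST up to 10; steps of 0.1), sign-free misses of the criterion a trigger run from AST 5.1 to 8.0. The smallest fold rise is 5.1 / 1.0 = 5.1. For these subjects the sign-free AST trigger moves from 5 to 8 × ULN.

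**3. Criterion d.** The same baseline condition appears in d, but e backs it up. If baseline AST ≤ 1 and AST > 3, then AST is more than 3 × its own baseline, so e is met: 0 misses on the grid. Only if e means an increase *of* 3 × (more than 4 × baseline) do misses appear, at baseline AST 0.8 to 1.0 and AST 3.1 to 4.0.

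**4. Testing the remedy for a.**

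| Case, no signs | As written | Same enzyme only | Baseline ALT or same enzyme |
|---|---|---|---|
| AST 0.8 to 7, ALT 1.1 | none | a | a |
| AST 1.5 to 7, ALT 0.9 (7 / 1.5 = 4.67-fold) | a | none | a |
| AST unchanged at 6, ALT 0.9 | a | none | a |

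The last column follows from logic: adding an alternative to the condition can only enlarge the set of results that meet a.

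**The case against.** **On the SAE rule.** The liver sentence in Section 7.6.5.7.1 sends the reader to Appendix 3, so the two could be read as threshold and reporting detail. But the pointer does not say that the definition is subject to an exception, and Section 7.6.5.7.2 requires SAE reports regardless of causality. The exception could also be taken to mean only the PT-INR footnote, yet the sentence covers the whole of criterion c and the footnote already deals with PT-INR.

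A reader might infer that a waived case receives only a liver form. The documents do not support that. Under Section 7.6.5.6 it is recorded as an AE and assessed for seriousness, which leads back to the definition in Section 7.6.5.7.1.

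**On criterion a.** The list of signs in d and e is illustrative and includes fever, so many such rises would meet e. Laboratory tests during treatment are symptom-driven (Section 7.6.4), so sign-free rises would surface mainly in routine-care draws or at End of Treatment, after dosing has ended. Sections 7.6.4.1, 7.6.5.1 and 7.6.5.6 still call for a clinical-significance review and treat new laboratory abnormalities as possible AEs. SAP Section 9.4 flags abnormal values in the listings. These points stand and narrow the effect. It would be wrong to say that such a rise goes unrecorded; what it loses is the mandatory trigger.

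**On what cannot be seen.** Figures in Appendix 3, apparently including its algorithm, are not shown. They might indicate which reading sites follow, but they cannot remove the difference between the visible sentences.

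**Conclusion.** Both parts hold in limited form and are worth correcting. The SAE conflict is confined to one situation: AST or ALT above 3 × ULN, TBL above 2 × ULN, and another explanation. At stake are whether an SAE report is filed and listed, and limits that differ by up to 48 hours. The criterion a miss is confined to AST above 5 and up to 8 × ULN from a normal baseline, with baseline ALT above ULN, no compatible sign, and normal TBL and PT-INR. Every such rise is more than 5-fold, and it is left to investigator judgement.

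Two stronger readings fail. Criterion d does not share the miss if e means more than 3 × the same enzyme's baseline. Nor does it follow that the baseline condition should simply be switched to the same enzyme, because that removes triggers the plan now has.

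The documents give no rate for such results, so no expected count is offered. The study plans up to about 18 subjects, and only safety reporting is affected, not any PK result. The conclusion rests on the visible text of Appendix 3.

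**What to change.** 1. **SAE rule.** Replace the criterion c sentence in Appendix 3 with: *AST or ALT > 3 × ULN with TBL > 2 × ULN must also be reported as an SAE. A case that meets criterion c only through PT-INR must be reported as an SAE unless an alternate explanation exists.* In Section 7.6.5.7.1 add a cross-reference to the PT-INR rule. Cost: a few more SAE reports, for bilirubin-arm cases with another explanation.

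2. **Criterion a.** Change the condition to: *if baseline ALT, or the baseline value of the same enzyme, is ≤ ULN*. This closes the miss and removes no trigger. Cost: some added Liver Event Forms and work-ups. It also leaves in place the existing trigger for an unchanged AST between 5 and 8 × ULN with normal baseline ALT. AST and ALT are both mandatory at Screening (Section 7.6.4.1.1), so no new test is needed.

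3. **Criteria d and e.** Leave d as it is. A same-enzyme rewrite would drop, for example, AST 1.5 to 4 × ULN with fever (4 / 1.5 = 2.67-fold), and would catch no new rise if e means more than 3 × baseline. If any edit is made, state in e that it means more than 3 × the same enzyme's baseline.

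4. **Editorial.** Section 4.5 cites Appendix 2 for the liver discontinuation criteria; it should cite Appendix 3.

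These are wording changes for one amendment, with no new subjects or analyses. SAP Section 11 suggests that enrolment may already be complete. If so, the sponsor can apply the Section 7.6.5.7.1 rule and check the listed laboratory data for the missed AST pattern.

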1. Glossary of Abbreviations

Abbreviation	Description
AE	Adverse Event
ALP	Alkaline Phosphatase
ALT	Alanine Aminotransferase
AST	Aspartate Aminotransferase
ATC	Anatomical Therapeutic Chemical
BAL	Bronchoalveolar Lavage
BALF	Bronchoalveolar Lavage Fluid
BLQ	Below the Limit of Quantification
BMI	Body Mass Index
CBC	Complete Blood Count
CRF	Case Report Form
CSR	Clinical Study Report
CrCl	Creatinine Clearance
CT	Computed Tomography
CV%	Coefficient of Variation
eCRF	Electronic Case Report Form
ELF	Epithelial Lining Fluid
EOI	End of Infusion
EOS	End of Study
EOT	End of Treatment
GGT	Gamma Glutamyltransferase
ICH	International Conference on Harmonization
IV	Intravenous
LLOQ	Lower Limit of Quantification
Max	Maximum
MedDRA	Medical Dictionary for Regulatory Activities
Min	Minimum
N/A	Not Applicable

This document is confidential.

Abbreviation	Description
PK	Pharmacokinetic(s)
PD	Pharmacodynamic(s)
PT	Preferred Term
q6h	Every 6 Hours
q8h	Every 8 Hours
QC	Quality Control
SAE	Serious Adverse Event
SAP	Statistical Analysis Plan
SD	Standard Deviation
SE	Standard Error
SI	Standard International System of Units
SOC	Standard of Care
SOI	Start of Infusion
SOP	Standard Operating Procedure
TEAE	Treatment Emergent Adverse Event
TLF	Table, Listing and Figure
TBL	Total Bilirubin
WHO	World Health Organization

This document is confidential.

2. Purpose

The purpose of this statistical analysis plan (SAP) is to ensure that the data listings, summary tables and figures that will be produced, and the statistical methodologies that will be used, are complete and appropriate to allow valid conclusions regarding the study objectives.

2.1. Responsibilities

Syneos Health will perform the statistical analyses.. Syneos Health will be responsible for the production and quality control of all tables, listings and figures (TLFs) with the guidance supplied by Shionogi Inc. The PK analysis will be carried out following this SAP with the guidance supplied by Shionogi Inc.

2.2. Brief Description

This is a phase 1b multicenter, single-arm, open-label study to assess the intrapulmonary and plasma concentrations of cefiderocol at steady state after multiple-dose administration in hospitalized subjects with known or suspected bacterial pneumonia on treatment with standard of care (SOC) antibiotics and requiring mechanical ventilation.

Screening of subjects will occur within 48 hours prior to administration of the first dose of cefiderocol on Day 1 of the study. A minimum of 3 (and up to approximately 18) qualified subjects will receive an initial 2-g dose (or renally adjusted dose as described in Table 1) of cefiderocol on Day 1 (within 72 hours of the start of potentially effective treatment with SOC antibiotics for bacterial pneumonia) and subsequently receive cefiderocol every 8 hours q8h (or q6h if subject has augmented renal function) with the dosage specified in Table 1.

Table 1 Cefiderocol Dosing and Bronchoalveolar Lavage Procedure for Various Degrees of Renal Function

Creatinine Clearance	Dosage	Number of Doses Prior to Performing BAL
Augmented renal function (CrCl \geq 120 mL/min) ^a	2 g, q6h, 3-hour infusion	3-6 doses
Normal renal function (CrCl < 120 mL/min) ^a	2 g, q8h, 3-hour infusion	3-6 doses
Mild renal impairment (CrCl 60 to < 90 mL/min) ^a	2 g, q8h, 3-hour infusion	3-6 doses
Moderate renal impairment (CrCl 30 to < 60 mL/min) ^a	1.5 g, q8h, 3-hour infusion	3-6 doses
Severe renal impairment (CrCl 15 to < 30 mL/min) ^a	1 g, q8h, 3-hour infusion	6-9 doses

BAL = bronchoalveolar lavage; CrCl = creatinine clearance; q8h = every 8 hours; q6h = every 6 hours

a Creatinine clearance will be calculated by Cockcroft-Gault equation at Screening.

The dose of cefiderocol administered to each subject will be determined by the investigator based on dosing recommendations (see protocol Section 5.2). End of Treatment (EOT) assessments will occur within 24 hours after administration of the last dose of cefiderocol, or at early termination. The End of Study (EOS) visit will occur 7 days (\pm 3 days), if there is no serious adverse event (SAE), after administration of the last dose of cefiderocol. For both cases the EOS visit can be performed on-site or by telephone (see Figure 1). If an SAE is observed it must be reported to Safety and all SAEs, regardless of causality, will be followed until resolution, stabilization, the condition becomes chronic, or the subject is lost to follow-up. The investigator will make an effort to collect adverse events (AEs) for 7 days after the last dose of study drug.

One epithelial lining fluid (ELF) sample for determination of cefiderocol concentrations will be collected by bronchoalveolar lavage (BAL) procedure at 3, 5, or 7 hours, depending on the ELF cefiderocol concentration data obtained, after administration of at least 3 doses of cefiderocol in subjects with normal or augmented renal function and subjects with mild or moderate renal impairment and after administration of at least 6 doses of cefiderocol in subjects with severe renal impairment. In addition, data from any BAL procedures performed during the study as part of routine patient care will also be collected as part of study data. A total of 4 blood samples for determination of plasma cefiderocol concentrations will be collected at prespecified time points corresponding to the dose after which the ELF sample is collected. Ongoing PK assessment of concentration data from both ELF and plasma samples will be performed for every 3 subjects to determine if modifications of the ELF sampling time point in subsequent subjects are needed.

All revised sampling time point modifications will be provided by the sponsor, discussed with the investigator, and documented (see protocol Section 7.5).

Blood and ELF samples will be collected also for determination of urea concentration. Urea is used as an endogenous marker of ELF because urea is small and relatively nonpolar and can travel across membranes freely to reach the outer surfaces of alveoli. The concentration of urea in ELF is considered to be same as the serum urea concentration, implying complete distribution. Therefore, the volume of ELF (V_{ELF}) is adjusted for excess exogenous volume using the concentration of urea in blood and ELF (see protocol Section 7.6.4.1.3).

Safety assessments including physical examinations, vital sign measurements, chest X-ray and clinical laboratory tests will be performed at prespecified time points prior to, during, and after administration of cefiderocol. In addition, data will be captured at various time points during the study from safety assessments (physical examinations, vital sign measurements, chest X-rays, and clinical laboratory tests) performed as part of routine patient care (see protocol Section 7.6). Date and result will be entered in the source documents and the eCRF. Adverse events will be monitored throughout the study from the time informed consent is obtained until 7 days after administration of the last dose of cefiderocol if there is no SAE.

Figure 1 Study Schematic

Screening	Cefiderocol Administration	End of Treatment	End of Study Visit ^a
Within 48 hours prior to the administration of the first dose of cefiderocol	Minimum of 3 doses (up to a total of 6 doses) in subjects with normal renal function and subjects with mild or moderate renal impairment, q8h; and with augmented renal function, q6h Minimum of 6 doses (up to a total of 9 doses) in subjects with severe renal impairment, q8h Initial dose must be within 48 to 72 hours of the start of treatment with SOC antibiotics for bacterial pneumonia	Within 24 hours after administration of the last dose of cefiderocol or early termination	7 days (\pm 3 days) after administration of the last dose of cefiderocol

qh8 = every 8 hours; q6h = every 6 hours; SOC = standard of care

^a End of Study Visit can be performed on-site or by telephone

A minimum of 3 subjects will be enrolled to provide a summary of cefiderocol concentrations in ELF in hospitalized subjects with known or suspected bacterial pneumonia being treated with SOC antibiotics and requiring mechanical ventilation. However, if necessary, up to approximately 18 subjects may be enrolled to ensure adequate information is obtained to meet the objectives of this study. Non-evaluable subjects will be replaced.

This document is confidential.

The maximum duration of study participation for an individual subject, from the time of Screening (within 48 hours prior to the administration of the first dose of cefiderocol) to the EOS visit (up to 7 days after administration of the last dose of cefiderocol), is 13 days. Cefiderocol dosing will be terminated once the BAL procedure has been performed and ELF samples, plasma PK samples, and urea samples have been collected for analyses at which time no further cefiderocol dosing will be permitted.

3. Study Objectives

